### **Randomization**

Multiple pharmacies are involved in participant enrollment--therefore, once informed written consent is obtained from the patient, the patients will be randomised by stratified randomization using a blocking factor to assign participants to either intervention or usual care groups.

Each participant will be assigned a unique identifier number and group allocation for the duration of their participation in the study--this unique identifier and allocation will also be communicated to and recorded by the pharmacy partner in the participant's patient profile to ensure consistency of the degree of pharmacist interventions described by the group the participant is allocated to.

The participant will be sent a secured electronic link (to the contact number or email they provided in the written consent form) that will include the participant's unique identifier and group allocation and the electronic version of the PHQ-9/GAD-7 questionnaire tool to complete and submit electronically. If the participant is unable to provide a means for the electronic link to be sent, the questionnaire tool can be completed with the pharmacist partner in person prior to their scheduled in-person/telehealth pharmacist meetings.

The study data (i.e. the participant's submitted electronic questionnaire tool results) will be sent directly to a centralised and secured website/database to ensure allocation concealment for the investigational team.

The participant questionnaire scores are available to the pharmacist partner via a secured electronic website/database prior to their scheduled in-person/telehealth meeting with the pharmacist partner.

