**Recruitment:**

Potential participants will be identified and approached by the pharmacist partners (pharmacists with APA and PraCID) if they are picking up or dropping off their prescription for a medication listed in Appendix 1 and 2.

Medication indication will be verified with the patient for the treatment of diagnosed MDD and/or GAD (and if additional verification is required--collateral from physician, Netcare consult note, or pharmacy record).

As part of the standard of pharmacist practice (as outlined in the Alberta College of Pharmacist Standards of Practice for Pharmacist and Pharmacy technicians [9]), a patient is clinically assessed for pharmacotherapy appropriateness by the pharmacist partner. This process is performed by the pharmacist partner and is the initial screen to determine if the patient meets any inclusion or exclusion criteria.

Determined by the pharmacist partner, if a patient meets the inclusion criteria for the study and does not meet any exclusion criteria, the patient will be asked if he/she wants to participate in the study and be provided with a formal invite letter to review.

If the patient agrees on participating, he/she will be asked to sign a written informed consent form. After signing the consent form, the patient will be enrolled in the study and randomised as a study participant using the secured electronic study website/database (developed by EPICORE and secured at the University of Alberta research office).

The participant's physician will receive the notification letter for physicians, from the pharmacist partner, to inform him/her that the participant has agreed to participate in the study. Should the physician refuse to have the participant participate in the study, the participant will not be enrolled into the study.

Should the participant decline recruitment into the study, they will continue to receive the same level of pharmacist care as outlined in the Alberta college of pharmacists standards of practice (9).

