## **Outcomes:**

### **Primary outcomes:**

The primary outcome is the mean score difference in PHQ-9 and GAD-7 scores from baseline to end of study participation, between the intervention and standard pharmacist care groups.

- Both PHQ-9 and GAD-7 are validated tools for measuring major depressive disorder and generalised anxiety, respectively, in the primary care setting. They are brief and can be self-administered, with similar results yielded with health care provider administered reports. These are desirable given the time restraints and competing demands we anticipate for community pharmacist partners participating in the study(11, 12).
- PHQ-9 scores reflect depression severity; Ranges from 0-27 (Scores: 0-4 none/minimal, 5-9 mild, 10-14 moderate, 15-19 moderately severe, 20-27 severe) (13).
- GAD-7 scores reflect anxiety severity; Ranges from 0-21 (Scores: 0-4 none/minimal, 5-9 mild, 10-14 moderate, 15-21 severe) (13)

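### The only baseline PHQ-9/GAD-7 is collected after randomisation, from participants who have been told their group, so the baseline part of the change score is open to reporting bias

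*Protocol*

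**What the plan says.** The order of events has to be put together from several sections of the Protocol.

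- **Recruitment:** "After signing the consent form, the patient will be enrolled in the study and randomised as a study participant using the secured electronic study website/database". No questionnaire comes between consent and randomisation.
- **Randomization, trigger:** "once informed written consent is obtained from the patient, the patients will be randomised by stratified randomization using a blocking factor". Consent is the only condition named.
- **Randomization, pharmacist:** "this unique identifier and allocation will also be communicated to and recorded by the pharmacy partner".
- **Randomization, participant:** the participant is sent a secure link containing the "unique identifier and group allocation and the electronic version of the PHQ-9/GAD-7 questionnaire tool to complete and submit electronically".
- **Randomization, fallback:** where no link can be sent, "the questionnaire tool can be completed with the pharmacist partner in person prior to their scheduled in-person/telehealth pharmacist meetings".
- **Randomization, concealment:** this is claimed for the investigational team only, not for the participant or the pharmacist partner.
- **Both Groups:** the questionnaire that is sent out is completed at month 0 and again before the month 6 visit.
- **Primary outcomes:** "The primary outcome is the mean score difference in PHQ-9 and GAD-7 scores from baseline to end of study participation", compared between groups.
- **Secondary outcomes:** response is a fall of at least 50% from baseline on each scale.
- **Analytical Plan:** intention to treat, last observation carried forward for missing data, and ANCOVA with covariates chosen by p < 0.25 between groups. The baseline score is not named as a covariate.

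**The concern.** A baseline is useful because randomisation cannot have influenced it. Here it can. The score is a self-report, given by someone who has just learned the group, or given in the presence of a pharmacist who knows it.

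The two groups also have different reasons to answer differently. At month 0 the intervention group is about to meet a pharmacist who will record the score and may change treatment in response to it. The control group receives no specific intervention.

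Any resulting difference in reported baseline enters the primary outcome through the subtraction, and enters the response outcomes through the 50% threshold. It cannot be separated from true baseline severity afterwards.

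There is also a gap in completeness. Randomisation does not wait for the questionnaire, so a participant can be randomised and never return it. That person belongs in an intention-to-treat analysis but has no change score, and nothing comes before a baseline that could be carried forward. Because the group is known when the form is requested, non-return could also differ between groups.

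**Working it through.** **1. The order of events.** A link that contains the group allocation cannot be sent before allocation. Both Groups says the sent questionnaire is the month 0 one. No section describes an earlier PHQ-9/GAD-7. The order is therefore consent, randomisation, disclosure of the group, baseline. No single sentence says so, but the sections allow no other reading.

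**2. The plan's own sample size.** Inputs from Sample Size Calculation: PHQ-9 difference 4.3, SD 6.9 (a baseline SD), 80% power, two-sided alpha 0.05.

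- Normal approximation: n = 2 × (1.960 + 0.842)² × (6.9/4.3)² ≈ 40.4, so 41 per group.
- t-test version: 41.4, so 42 per group and 84 in total, as stated.
- Inflation: 42/0.90 = 46.7, so 47 per group and 94 in total, as stated.

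The PHQ-9 figure reproduces and is not in dispute.

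**3. How large the bias could be.** The documents give no size for a reporting shift. Assume that knowing the group changes the difference in mean baseline PHQ-9 between arms by b points (0.5, 1 or 2), leaves month 6 untouched, and that the true effect is zero.

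*Unadjusted change score.* The bias is b. SE = 6.9 × √(2/42) = 1.506, taking the SD of change as 6.9. If baseline and month 6 have equal SDs, that corresponds to a correlation of 0.5, since 6.9 × √(2 × (1 − 0.5)) = 6.9.

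*ANCOVA with baseline as covariate.* The slope equals the correlation r when the SDs are equal, so the bias is r × b. SE ≈ 1.506 × √(1 − r²), which is 1.304 at r = 0.5.

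*Two-sided false-positive rate* = Φ(bias/SE − 1.96) + Φ(−bias/SE − 1.96).

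| Shift b | Share of 4.3 | Change score | ANCOVA r = 0.3 | ANCOVA r = 0.5 | ANCOVA r = 0.7 |
|---|---|---|---|---|---|
| 0.5 | 12% | 6.3% | 5.1% | 5.4% | 6.2% |
| 1 | 23% | 10.2% | 5.5% | 6.7% | 10.0% |
| 2 | 47% | 26.4% | 7.0% | 12.0% | 25.6% |

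Worked line for b = 2. Change score: 2/1.506 = 1.328, giving Φ(−0.632) + Φ(−3.288) ≈ 0.264. ANCOVA at r = 0.5: 1.0/1.304 = 0.767, giving Φ(−1.193) + Φ(−2.727) ≈ 0.120. An exact t-test for the change score gives 6.2%, 10.1% and 25.9%, so the approximation is adequate.

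**4. Response outcomes.** A participant who reports 15 at baseline must reach 7 or lower to have halved the score. One who reports 16 needs only 8 or lower. One point of baseline reporting therefore moves the threshold.

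**5. Is adjustment assured?** ANCOVA is named, but covariates enter only if they differ between groups at p < 0.25, and the baseline score is not singled out. Whether the change-score column or an ANCOVA column applies is therefore not settled by the Protocol.

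**The case against.** Several points on the other side have force.

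- **The planned analysis is ANCOVA, so the change-score rates may overstate the problem.** This stands in part. At correlation 0.5 adjustment halves the bias, and the rates are 5.4%, 6.7% and 12%. But adjustment does not remove the bias, and the Protocol does not guarantee it.
- **Direction and size are unknown.** This stands. A reader might infer that the trial is tilted towards the intervention. The documents do not support that. Intervention participants who rate themselves worse before meeting a prescriber would favour the intervention; disappointed control participants who rate themselves worse would count against it. The two could cancel.
- **The form covers the last two weeks, and what is at issue is knowledge of the group rather than treatment received.** This is fair, and it argues for a smaller shift, but it does not make a self-report immune to what the respondent has just been told. The assisted route applies only where no link can be sent. Primary outcomes says that self-administered and provider-administered results are similar, but that does not address a provider who knows the group.
- **Month 6 is open-label anyway.** This is true. A reader might conclude that the group should also come out of the month 6 link. That would achieve little, because by then the participant has known the group for six months. The baseline is the measurement that can be fully protected.

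Two further readings are tempting but not supported. One is that the late PHQ-9 undermines the exclusion of severe depression. The exclusion criteria give no PHQ-9 cut-off, and Recruitment leaves eligibility to the pharmacist's clinical assessment before consent. The other is that the assignment itself is compromised. Nothing here affects the sequence; the issue is reporting after randomisation.

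**Conclusion.** The point holds as an avoidable weakness in procedure. Followed as written, the Protocol yields an unblinded, post-randomisation baseline for the primary outcome and for the 50% response outcomes, and it can leave randomised participants with no baseline at all.

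The size is illustrative only. For assumed shifts of 0.5 to 2 points, the two-sided false-positive rate runs from about 6% to 26% for an unadjusted change score, and from about 5.4% to 12% for ANCOVA on baseline at correlation 0.5. This rests on 42 per arm, on the cited baseline SD of 6.9 being used for both time points and for change, and on a shift that touches only the baseline. The documents fix neither the shift nor the correlation, nor do they give a rate of unreturned baselines. The illustration shows what the design is exposed to and does not predict a bias of any particular size. No analysis can fully recover a clean baseline once participants have been enrolled in this order.

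**What to change.** In Recruitment and Randomization, restate the order as:

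1. written consent;
2. baseline PHQ-9/GAD-7 submitted in the study database;
3. randomisation released by the database only once that baseline is recorded;
4. allocation disclosed to the pharmacist partner and the participant.

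Take the group allocation out of the baseline questionnaire link. Participants who cannot use a link can still complete the form with the pharmacist partner, who at that stage will not know the group.

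This also closes the completeness gap, since nobody is randomised without a baseline.

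The cost is a change to the database workflow, a short edit to those two sections, and a few minutes at enrolment before the group is released. The sample size is unchanged at 84, or 94 after inflation. The change does not remove open-label reporting at month 6, and the trial report should say so.

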**1) Patient Assessment:**

- Recording participant scores from the combined PHQ-9/GAD-7 questionnaire tool (Appendix 4) completed by the participant, which includes:
  - PHQ-9 (Patient Health Questionnaire 9-item), a multipurpose instrument for screening, diagnosing, monitoring and measuring the severity of depression
  - GAD-7 (Generalised Anxiety Disorder 7-item)
- If determined clinically relevant by the pharmacist partner will assess:
  - appearance, current mood, sleeping patterns, mental health, medical history, social history, family history, relationships with others, suicidal ideation, previous suicide attempts or hospitalizations, current employment status.

2) Pharmacist-initiated prescribing dose adjustment, medication change to different medication, deprescribing, or prescribing adjunctive add-on medication, to achieve clinical response and/or remission of MDD and/or GAD and establish appropriate cognitive/functional status as per CAMAT guidelines (7, 8).

3) Provide regular communication updates with the patient's family physician after each contact with the patient (via fax or electronic charting).

4) Providing medication counselling and educational support to the participant.

5) Identification of adverse drug effects, drug interactions, or severe deterioration (i.e. suicide attempt)

6) Interim telephone/telehealth follow-up conducted by the pharmacist partner since the last in-person follow-up & a minimum of 1-2 weeks after the last in-person follow-up that involved a dose adjustment, prescribing of adjunctive medication, or discontinuation of therapy. (Note: a telephone follow-up does not replace the scheduled in-person/telehealth follow-up).

7) Collaborate with physician to arrange referral to psychologist, psychiatrist, counsellor or social worker for psychotherapy

Should the participant from the interventional group drop out or complete the 6 month study period, they will be offered to continue with similar interventional care or standard pharmacist care but no data will be collected since their dropout or following study completion.

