**Both Groups**

- Indication of medication (i.e. MDD, GAD, or both) will be recorded by the pharmacist partner in the secured study electronic website/database.
- The electronic PHQ-9/GAD-7 questionnaire (Appendix 4) will be sent securely to and completed by the participant at enrollment (month 0) and prior to the participant's in-person scheduled month 6 (final). The questionnaire results will be available to the study investigator and pharmacist participants but linked only to the participant's study ID.
- Participants will receive a pamphlet copy of Alberta Health Services Access Mental Health resource pamphlet "Know Your Addiction and Mental Health Options" which provides information regarding walk-in services, crisis support, and urgent care (10). An equivalent alternative pamphlet can be developed and provided by the study team if this document becomes obsolete or additional update/information is required.

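### The fallback for participants without an electronic link has them answer the primary-outcome questionnaire with the unblinded treating pharmacist: probably a small bias, but an avoidable one

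*Protocol*

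**What the plan says.** Outcomes, Primary outcomes: "The primary outcome is the mean score difference in PHQ-9 and GAD-7 scores from baseline to end of study participation", compared between the two groups. The section Both Groups has the questionnaire "completed by the participant at enrollment (month 0) and prior to the participant's in-person scheduled month 6 (final" assessment, in both arms.

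Randomization sets out two routes. The default is a link to "the electronic version of the PHQ-9/GAD-7 questionnaire tool to complete and submit electronically", sent to the phone number or email given at consent. For participants who can supply neither, "the questionnaire tool can be completed with the pharmacist partner in person prior to their scheduled in-person/telehealth pharmacist meetings".

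The same section says of the pharmacy that "this unique identifier and allocation will also be communicated to and recorded by the pharmacy partner in the participant's patient profile". The participant knows the arm too, because the link "will include the participant's unique identifier and group allocation".

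The pharmacist partner carries out the intervention. The Intervention Group section schedules contacts at months 0, 1, 3 and 6, and the numbered list of interventions adds "Interim telephone/telehealth follow-up conducted by the pharmacist partner since the last in-person follow-up". The Control Group section provides standard care only.

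Two statements could be read as safeguards. Randomization says that central electronic submission keeps the investigational team unaware of allocation. Primary outcomes says of the instruments: "They are brief and can be self-administered, with similar results yielded with health care provider administered reports".

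**The concern.** In the fallback, the person whose care is under test takes part in collecting the primary outcome and knows the participant's arm. Neither possible safeguard covers this. The concealment sentence concerns the investigators and electronic submissions, not the pharmacist or the in-person route. The equivalence statement concerns mode of administration and says nothing about a provider who knows the arm and gave the treatment.

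The influence could differ by arm because the relationship does. By month 6 an intervention participant has had several scheduled meetings and possibly interim calls with this pharmacist, and a control has had standard care. The items in Appendix 4 cover low mood, self-worth and thoughts of self-harm, which are sensitive to answer in front of one's own carer. Any differential pull would enter the PHQ-9 and GAD-7 comparison directly, and also the response and remission outcomes built on the same scores.

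**Working it through.** **Inputs from the Protocol** (Sample Size Calculation): PHQ-9 SD 6.9, GAD SD 5.8, PHQ-9 target difference 4.3 points, 80% power, two-sided alpha 0.05, 42 per group before inflation.

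**The plan's own figure.** The normal approximation gives n = 2 × (1.960 + 0.842)² × (6.9/4.3)² = 40.4, so 41 per group. The noncentral t calculation gives 42 per group (power 80.6%), which matches the Protocol. Allowing for 10% loss, 42/0.9 = 46.7, so 47 per group, also as stated. The PHQ-9 calculation fixes the trial's size, so its 4.3 points is the yardstick below.

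**Bias formula.** Let f be the share of participants using the fallback, expected to be equal in both arms under randomisation. Let b be the extra differential shift: the between-arm difference in how far answering with the pharmacist moves the change score, over and above what happens with the link. Then

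bias in the arm difference = f × b.

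**Effect on the test.** With 42 per group, SE = 6.9 × √(2/42) = 1.506 points for PHQ-9 and 5.8 × √(2/42) = 1.266 for GAD-7. If there is no true effect, the rejection probability is

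1 − Φ(1.96 − f·b/SE) + Φ(−1.96 − f·b/SE).

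**Results.** The Protocol gives neither f nor b, so every value of both is an assumption.

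| f | b (points) | Bias (points) | Share of 4.3 | Type I error, PHQ-9 | Type I error, GAD-7 |
|---|---|---|---|---|---|
| 2% | 1 | 0.02 | 0.5% | 5.00% | 5.00% |
| 5% | 3 | 0.15 | 3.5% | 5.11% | 5.16% |
| 10% | 1 | 0.10 | 2.3% | 5.05% | 5.07% |
| 20% | 2 | 0.40 | 9.3% | 5.81% | 6.15% |
| 30% | 3 | 0.90 | 20.9% | 9.18% | 10.96% |

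Thus 2-5% use with a 1-3 point shift gives 0.02-0.15 points, and 10-30% use gives 0.1-0.9 points. Only heavy use together with a large shift affects the error rate noticeably.

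**What cancels.** A mode effect that is the same at month 0 and month 6 drops out of the change score. A mode effect common to both arms drops out of the comparison. What remains is an arm-specific shift that builds up with contact by month 6, and b stands for that part alone.

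**The case against.** The strongest objection is that the trigger is narrow. A phone number or an email is enough to receive the link, follow-up includes telephone contact, and people unable to attend regular follow-up are excluded. Users of the fallback should be few, and nothing in the Protocol points to 10-30%. This stands. The Protocol does select pharmacies partly for serving rural, inner-city and elderly patients, so use need not be negligible, but it gives no figure.

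A reader might infer that the unblinded pharmacist rates the outcome. The text does not support that. It says the tool is completed with the pharmacist, the Both Groups section describes completion by the participant, and Appendix 4 has fixed self-report items that are summed. Presence or assistance is the most that can be read into it.

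A reader might also infer that removing the fallback would free the outcome of bias. It would not. Participants using the link know their arm, and the same pharmacist sees their scores before the meeting. Only the increment from answering in the pharmacist's presence is at issue. Its direction, though more likely to favour the intervention, is not established by the documents.

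Finally, a fallback of some kind is useful. It avoids missing primary data, which the Analytical Plan would fill by last observation carried forward. This argues for changing how the fallback works, not for deleting it.

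**Conclusion.** The point holds in a limited form. For a probably small group of participants, the Protocol places the unblinded treating pharmacist with the participant while the primary outcome is answered, and no stated safeguard covers this. The effect could differ by arm because contact does. Its size cannot be known from the documents: about 0.02-0.15 PHQ-9 points if 2-5% use the fallback and 0.1-0.9 points if 10-30% do, both on an assumed 1-3 point extra differential shift, against a 4.3-point target. The lower range seems more plausible given the narrow trigger. The Protocol does not support a claim that the primary comparison is materially biased, or that type I error will approach 9%. The case for change is that the influence is avoidable at almost no cost, and that mode of completion cannot be reliably reconstructed later if it is not recorded.

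**What to change.** In Randomization, replace the fallback sentence. Participants without a link complete the same tool themselves, unassisted, on paper or an available pharmacy device before the meeting, at least for the month 0 and month 6 outcome assessments. Responses are then entered in the study database so that the pharmacist can still see the scores before the meeting, as Randomization and Recording interventions require. A sealed form returned centrally would not meet that requirement unless it were entered in time.

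Use the same mode at month 0 and month 6 where possible, and add one data field for the mode and any assistance given.

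The cost is one sentence, a paper form or an existing device, one data field and a little data entry. Sample size is unchanged and no blinded assessor is needed. The downside is that a few participants who need reading help would be helped by someone other than the treating pharmacist where possible, and otherwise flagged in the same field.
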